### 7.2 PARTICIPANT DISCONTINUATION/WITHDRAWAL FROM THE STUDY

Participants may withdraw from the study at any time; likewise, the study team can withdraw a participant from the study given any of the following reasons:

- Individual expresses desire to stop participation.
- A new or exacerbated clinical occurrence or adverse event that precludes safe and meaningful participation in the remaining study activities (note: while it may be necessary for a participant who experiences an adverse event to discontinue study treatment, they do not necessarily need to be withdrawn from the study).

- This criterion can include, but is not limited to, an adverse event, disease progression, other medical condition or lab finding.
- Individual fails to comply with study requirements (e.g., unable or unwilling to complete lab exams, outcome assessments, lost-to-follow up, maintain appropriate communications with the study team, etc.)
- Study team discretion that continued participation is unlikely to be safe and/or meaningful.
- Participant status changes such that an individual no longer meets eligibility criteria.

The reason for withdrawal will be documented in the study record (i.e., CRFs and REDCap database). Participants will be informed that they have been withdrawn from the study by the study team.

### **Replacements**

- Participants who sign the informed consent form but do not receive the study intervention (for whatever reason, e.g., if they change their mind) will be replaced.
- Participants who sign the informed consent form, *and* receive the study intervention, *and* subsequently are *withdrawn or discontinued from the study*, may be replaced at the discretion of the PI and Co-Is.

## **7.3 LOST TO FOLLOW-UP**

Every effort will be made to maintain contact throughout an individual's enrollment. Standard practice for participant contact can involve telephone calls, routine emails, and snail mail letters, and will include a review of the EMR to check health status prior to attempting contact. The exact number of encounters will be based on study team discretion and knowledge of the participants, with consideration of the following guidelines:

### **Schedule baseline visit**

- Initial introduction letter and 3 calls without contact.
- Unlimited, yet practical, number of calls in context of contact with individual.

### **Bi-weekly phone calls**

- 5 encounter attempts made at different times.
- Can use email if preferred by participant.
- Send letter asking for participant to call or email study team if no contact made after 3 attempts.

### **Second Visit**

- Phone calls in the month preceding the projected follow-up window.
- Can use email if preferred by participant.
- Send letter asking for participant to call or email the study team if no contact is made.
  - Provide alternatives to facilitate completing outcome assessments: surveys over phone, urine analysis done at a clinic closer to home, etc.

Since some of the information to be collected for this follow-up may be available in participants' medical records, e.g., documentation of treatment for a UTI, study staff will review records before contacting subjects and query subjects if discrepancies are observed. If the follow-up cannot be completed with the subject, data from their medical record may be entered into the study database. All encounters will be documented in the study record. Individuals who are deemed "unreachable" will be withdrawn from the study and categorized as "Lost-to-follow up."

Participants will be asked if they would like to participate in a brief survey about their experience in the trial. When possible, these questions will be asked at the end of their follow up. For those who already completed their third follow up, the study team will contact them via phone or e-mail asking the same questions. Three to four contact attempts will be made to participants to gauge their interest in completing this post-intervention survey. Email may be used if preferred by participant. If a participant cannot be reached after these attempts they will be considered uninterested in the survey. All participants will be thanked for their participation in the study either verbally or by letter.

## 8 STUDY ASSESSMENTS AND PROCEDURES

### 8.1 EFFICACY ASSESSMENTS

*Section 8.1 refers to lab visits and study interviews. It will be standard practice to conduct as many procedures remotely as possible to better protect subject/caregiver(s) and UM staff against the risk of COVID-19. However, in cases where a procedure cannot be conducted remotely (e.g., required in-person lab visits for blood draws), the study coordinator will educate study participants/caregivers on all of Michigan Medicine's safety guidelines for entering and being in UM buildings (e.g., COVID screenings, PPE, social distancing, etc.).*

**Demographics, Clinical History and Current Medications** will be abstracted from the electronic medical record and confirmed with participant and caregiver during study interviews. Co-morbidities, bladder and bowel symptoms, and current medications will be recorded. Elements specific to SCI include age at injury and level and completeness of neurological impairment. Changes in health status and medication use will be updated during each interview.

**Urine analysis** – Prior to any MLabs visit, the study coordinator will remind the participant of Michigan Medicine's policies regarding COVID-19 as they relate to the participant and any person whom they might need to accompany them. Participants will provide urine samples according to MLabs (Michigan Medicine Pathology Handbook) specifications. A clean urine analysis is required for enrollment. Minimum volume required is 0.5ml collected in a non-sterile plastic urine cup. Dipstick analysis may be performed in the clinic at the time of the baseline visit; results are usually available within 10-15 minutes. Tests that come back positive will be sent to the lab for a urine culture. Specimens can be stored at room temperature if received in lab within 2 hours of collection; otherwise the sample should be refrigerated for up to 24hr. Results are usually back within 4 days for a culture.

**Self-reported quality of life measures** will be collected twice: at baseline and after the treatment period (approximately six months). Several disease-specific and overall quality of life measures will be used, including several scales from the SCI-QOL Measurement System. The SCI-QOL system builds on the PROMIS and Neuro-QOL initiatives were developed to address a dearth of valid patient-reported outcome measures for patients with spinal cord injury.

- *Neurogenic Bladder Symptom Score (NBSS)*: 22 item validated measure that assesses symptoms across three domains (incontinence, storage & voiding, and consequences) plus one overall quality of life item.
- *Neurogenic Bowel Dysfunction Score (NBD)*: 10 item validated measure that assesses frequency, of defecation and methods of bowel management and complications.
- *SF-Qualiveen*: 8 item validated measure for urinary disorders that covers four domains (bother with limitations, frequency of limitations, fears, and feelings). Participants respond to each item using a 5-point Likert scale.

- SCI-QOL Measurement System's *Bladder Management Difficulties, Bladder Complications and Bowel Management Difficulties*: these reflect three scales within the SCI-QOL battery that is part of the NIH Patient Reported Outcomes Measurement Information System (PROMIS) initiative. The short form for each scale will be administered (range 5-9 items).
- SCI-QOL Measurement System's *Satisfaction with Social Roles and Activities* is a 10-item short-form that is also part of the overall SCI-QOL battery.
- *Community Participation Indicators Scale*: 20 item validated measure of the frequency and importance of involvement in various types of activities.

**UTI Query and Adverse Event Occurrences** – Study staff will review the participant's EMR and communicate with them to query for UTI symptoms and occurrences, and any adverse events and side effects every 2 weeks throughout the study. These contacts also serve to promote protocol adherence and compliance with the study schedule, and will occur through remote video interviews, or over the phone. In addition, participants are instructed to contact the study team at any time during the trial to report UTIs, UTI symptoms, AEs, and any other concerns (e.g. transportation challenges or schedule conflicts). Each contact, whether scheduled or ad hoc, will be documented in the study record. Study staff will also query for UTI occurrences at Visit 3 (three months after the end of treatment).

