## 2.3 RISK/BENEFIT ASSESSMENT

### 2.3.1 KNOWN POTENTIAL RISKS

The overall risk of intravesical gentamicin for the management of recurrent UTIs in patients with neurogenic bladder is low. The method of daily bladder instillations is a common clinical strategy at Michigan Medicine, Department of Urology for specific patients (i.e. those with neurogenic bladder and frequent symptomatic UTIs), and it is one that is generally well-received by both patients and care givers. A retrospective analysis of Michigan Medicine patients showed mild and rare adverse events while using Gentamicin bladder instillations. Likewise, Abrams et al. and Defoor et al. suggest that gentamicin as prophylaxis against recurrent UTIs is well-tolerated and of minimal risk.

*Urinary tract infection (primary outcome)* – Recurrent UTIs are a likely occurrence in this study population. Participants will be instructed to contact their physicians at U-M who provide urological care in the event of UTI symptoms and can expect to be managed according to standard clinical practice (e.g. a course of oral antibiotics). The study team will query participants bi-weekly for any UTI occurrences (including symptoms and treated cases) and prompt the participant to follow-up accordingly if they have not already done so.

*Risks associated with regular bladder catheterization* – There is *potential for trauma at the site of insertion* of the catheter. The risk associated with participation in this study is no greater than experienced by these patients as part of their typical catheterization process. Likewise, there is *a risk of contamination from using non-sterilized equipment*. Again, this risk is commensurate with participant's risk exposure during their typical catheterization process. Participants and/or their caregivers will typically be experienced in the proper and safe manner of clean intermittent catheterization, but all will receive education and guidance in proper and hygienic catheterization practices with their study materials.

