#### HYPOTHESES

The proposed study is a pre- post CT in which participants receive the study drug for six calendar months, and analysis compares their frequency of UTIs during this period to the frequency in the prior six months:

1. The incidence of UTIs will be lower during the treatment period than it had been during the previous six calendar months. Occurrence of UTIs throughout this study will be defined as having symptoms of a UTI, followed by a positive urine culture and prescribed treatment.
2. The number of bladder and bowel complications will be likewise decreased during the treatment period compared to what was reported during the baseline interview.
3. Reported health-related quality of life will be higher during the treatment period compared to the how it was reported during the baseline interview.
4. Satisfaction with social roles and activities and community participation will be higher during the treatment period than how it had been reported during the baseline interview.

 Throughout this document, six months refers to 180 calendar days.

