### 5.1 INCLUSION CRITERIA

The electronic medical record (EMR) will be pre-screened for all inclusion criteria prior to the baseline interview and initial lab work. Criteria will be confirmed by patient or caregiver report at the screening assessment.

- Provision of signed and dated informed consent form.
- Male or female 18 years or older at time of enrollment.
- History of traumatic SCI or non-traumatic spinal cord disease (SCD), with sustained neurological dysfunction. Traumatic and non-traumatic SCI/D are defined according to the International SCI Standards and Datasets.
- At least 6-months post-initial hospital discharge following SCI/D onset.
- Neurogenic bladder.
- Ability to self-perform daily instillation or with help of others and willingness to adhere to the study regimen.
- Negative pregnancy test (for females of childbearing age) and expresses willing and ability to use appropriate contraception while enrolled in the study.
- History of at least 2 UTIs documented in the EMR during the previous six months (prior to screening).
- Have a designated physician or health care provider for routine urological care who is a member of Michigan Medicine.
- Use of clean intermittent catheterization (CIC) or catheterization through a stoma (i.e. Mitrofanoff) as their primary method of bladder management
- Agreement to adhere to Lifestyle Considerations (see below) throughout participation in the study and to complete the daily dosing log as instructed by the study coordinator.

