### 9.2 SAMPLE SIZE DETERMINATION

Power calculations were conducted based on the **primary hypothesis that incidence of UTIs will be significantly lower during the treatment period (gentamicin + saline) than during the prior six months.**

In calculating power, we assume that during the study period, there will be a 50% reduction in UTIs from the number that participant experienced during the prior six months, which serves as the control period. These assumptions are based on the findings of a six-month retrospective study of gentamicin. Calculations of power were conducted assuming that paired samples t-tests will be used to assess the first hypothesis. While we may consider using other additional ways of determining differences in UTIs between the baseline and trial periods, paired samples t-tests will be used at least initially. Because we are working with count rather than continuous data, the t-tests will be conducted using natural log-transformed infection rates rather than the raw rates. Based on our assumptions, the sample size needed to have a power of at least 80% will be 15. This is the necessary sample size of participants who complete the study. SPSS version 28 was used to conduct this power analysis.

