## 9.4 STATISTICAL ANALYSES

### 9.4.1 GENERAL APPROACH

All data will be examined for completeness and outliers before hypothesis testing. Categorical data will be summarized in terms of frequencies, presented as n (%), and continuous data will be summarized in terms of means (standard deviations). Participant demographics and clinical status will be evaluated using descriptive statistics. These analyses will be conducted after all data has been collected. All efforts will be made to recruit a balanced sample representative of persons with SCI/D. Missing data will be handled using common statistical methods such as multiple imputation and the estimation maximization approach.

All statistical procedures will be run using either SPSS or the statistical package R. Statistical significance will be set at  $p < 0.05$  for group comparisons and all models.

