#### 10.1.9 DATA HANDLING AND RECORD KEEPING

##### 10.1.9.1 DATA COLLECTION AND MANAGEMENT RESPONSIBILITIES

Day-to-day data collection and management will be the responsibility of the study coordinator(s) or other study staff, with the project manager ([name], MPP) providing managerial and statistical oversight. Source data are defined as:

- Survey responses of participants whether via electronic direct-entry or using paper and pencil

- EMR for enumeration of UTIs documented on appropriate case report form (CRF).
- Participant dosing log for compliance with medication protocol.
- Participant-report of clinical status updates and data regarding concomitant medication will be recorded on the appropriate case report form.
- Adverse events as reported by participant or as indicated in the EMR will be documented on the appropriate case report form.

All CRFs and study documents will be completed electronically except for participants dosing logs, reviewed for accuracy, and stored in the participant research record within the secured database.

All study data (e.g., outcome data, encounter records, adverse events, etc.) will be stored in a REDCap database supported by the Michigan Medicine IT infrastructure. Data base quality checks will be conducted by the project manager and/or study coordinator to determine missing information, and data inconsistencies.

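### Two-weekly queries and prompts to seek care operate on treatment but not before it, so the before-after UTI ratio mixes detection with drug effect and most likely understates benefit

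*Protocol*

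**What the plan says.** Protocol Section 4.1 compares each participant's UTIs over six months of treatment with the six months before it, six months being 180 days. There is no control arm. The SAP expresses the comparison as incidence rate ratios against the pre-treatment period.

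**On treatment.** Section 8.1: "Study staff will review the participant's EMR and communicate with them to query for UTI symptoms and occurrences", every two weeks. Section 2.3.1 says that staff will also "prompt the participant to follow-up accordingly if they have not already done so". Section 8.2 has those reporting a UTI or symptoms advised to see their provider. The Schedule of Activities adds a study-paid urinalysis at Visit 2, cultured if positive. Section 8.3.4 ties the calls to the intervention period.

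**Before treatment.** Section 5.1 requires "History of at least 2 UTIs documented in the EMR during the previous six months (prior to screening", with criteria checked by patient or caregiver report at screening. Section 8.1 has clinical history taken from the record and confirmed at interview. No calls or prompts cover this period.

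**Common to both.** Section 4.1 (Hypotheses) defines a UTI, for the whole study, as symptoms "followed by a positive urine culture and prescribed treatment". Section 10.1.9.1 lists as source data "EMR for enumeration of UTIs documented on appropriate case report form (CRF", without limiting this to one period.

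Neither Sections 9.2 to 9.4.3 nor the SAP mentions the difference in surveillance. The one sensitivity analysis foreseen (Section 9.4.3) concerns missing data.

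**The concern.** Two of the three elements of a UTI, a positive culture and a prescription, exist only if the participant reaches care. A call every two weeks that asks about symptoms and urges follow-up makes that more likely. Some episodes that would have passed unrecorded before enrolment become countable on treatment. Taking both counts from the medical record does not remove this, because the prompt changes what enters the record.

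With no concurrent control, a shift in detection goes straight into the primary ratio. At stake are the size of the reported effect and the power of a trial planned around 15 completers.

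**Working it through.** **Inputs from the documents.** Section 9.2 assumes that "there will be a 50% reduction in UTIs from the number that participant experienced during the prior six months" and concludes that "the sample size needed to have a power of at least 80% will be 15", using a paired t-test on natural-log rates. Section 9.4.1 sets significance at p < 0.05; sidedness is not stated and two-sided is taken here. The documents give no SD of the within-person log difference, no baseline rate and no detection probabilities, so all detection figures below are assumptions.

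**Step 1: the plan's own figure.** N = 15 can be neither confirmed nor refuted without the SD. Solving the noncentral t power equation for 80% at n = 15 and ln(0.5) = -0.693 gives SD = 0.89 (standardised effect 0.693/0.891 = 0.78). That SD is carried forward.

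**Step 2: effect on the ratio.** Let k = detection on treatment / detection before. Then observed ratio = true ratio × k. With a true ratio of 0.50 and 95% detection on treatment:
- 90% before: 0.50 × 0.95/0.90 = 0.528
- 80% before: 0.50 × 0.95/0.80 = 0.594, an apparent reduction of 41% instead of 50%
- 70% before: 0.50 × 0.95/0.70 = 0.679

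Read backwards, an observed 0.50 would mean a true 0.50/1.2 = 0.42 at k = 1.2.

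**Step 3: effect on power** (true ratio 0.50, SD held at 0.89, two-sided):

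| k | Observed ratio | Power at n = 15 | n for 80% |
|---|---|---|---|
| 1.0 | 0.50 | 80% | 15 |
| 1.1 | 0.55 | 68% | 20 |
| 1.2 | 0.60 | 54% | 26 |
| 1.25 | 0.625 | 48% | 31 |
| 1.5 | 0.75 | 21% | 78 |

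Cross-check on the SAP's rate-ratio scale: an exact conditional test of two Poisson totals, n = 15, no overdispersion. With an assumed baseline mean of 2 UTIs per six months, power falls from 56% at k = 1 to 36% at k = 1.2. With a mean of 3 it falls from 76% to 52%.

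**Step 4: direction.** For a drug with no effect the observed ratio equals k. If active search raises detection, k exceeds 1 and the result is an apparent increase in UTIs, not a benefit.

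**Step 5: what the proposed bracket would show.** Take 100 true UTIs before and 50 during treatment, with 80% and 95% detection. Recorded counts are 80 and 47.5, ratio 0.594. Without prompting, 50 × 0.80 = 40 would have been recorded, ratio 0.50, so 7.5 events are due to prompting. If 10 events are flagged (those 7.5 plus 2.5 that would have reached care anyway), the ratio without them is 37.5/80 = 0.469. The pair 0.47 to 0.59 encloses the true 0.50.

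**The case against.** The plan already narrows the gap. One definition and one record source are named. Section 5.1 selects people with a Michigan Medicine urological provider and at least two recorded UTIs, and Section 5.3 expects them to consult physicians about symptoms. Prompts can add only the episodes such people would have left untreated. The Visit 2 test also has a partial counterpart in the screening urinalysis, and a positive culture without symptoms and treatment would not meet the definition. All of this stands. It limits how far k is likely to exceed 1, but does not bring it to 1: the calls and prompts still have no pre-treatment counterpart.

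A reader might go further and infer that baseline events need only be in the record while on-treatment events must meet all three elements, which could produce a false benefit. The documents do not support that. Section 5.1 is an eligibility criterion, not a counting rule. Section 4.1 gives its three-part definition for the whole study, directly after naming both periods. It would help to say expressly that the definition governs the pre-treatment window, but that is clarification. Nor does the baseline history come from records alone, since patient or caregiver confirmation is required, although that too is retrospective.

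One ambiguity remains. Section 5.5 describes the calls as a means of collecting UTI information, and neither document says whether a UTI reported on a call but absent from the record counts.

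**Conclusion.** The point holds in this form: surveillance is more intensive on treatment than in the comparison period, it can act on the endpoint through care-seeking, and neither document handles it. The primary ratio estimates drug effect times k. The most likely direction is understated benefit and lost power: a true 0.50 appears as 0.53 to 0.68 under the assumed detection rates, and power falls from 80% to about 54% at k = 1.2.

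These figures rest on assumed detection rates, an SD solved to match the plan's own sample size, and that SD staying constant as k changes. The true k cannot be found from the documents.

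This difference in detection would not explain away a positive result. That statement covers detection only; it does not make the before-after comparison conservative as a whole.

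**What to change.** In the SAP:
- Count both 180-day windows by the same medical-record abstraction, applying the three-part definition of Section 4.1 to every event. Call-only reports then stay out of the primary count.
- Flag each on-treatment event first raised by a study contact or found by the Visit 2 test. Flag an event found by the screening urinalysis likewise if that test falls in the pre-treatment window.
- Report the rate ratio with and without flagged events, as a bracket.
- State how UTIs are ascertained in the SAP's one- and six-month post-treatment periods. For the time after treatment, Section 8.1 specifically names only a UTI query at Visit 3.

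The cost is a SAP paragraph and one coded variable. The SAP is written in the past tense, so flags would have to be coded from the contact records that Section 8.1 already requires. Excluding flagged events also removes some that would have reached care anyway, so that ratio leans towards the drug and should be read as a bound, and only as far as the contact records are complete. An analysis adding participant-reported events is not advised: they are captured prospectively in one period only and would recreate the imbalance.
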